Appendix 6 Management Rules for Amyloid-Related Imaging Abnormalities

Event	Characteristics	Action to Be Taken
ARIA-E	Asymptomatic ARIA-E and BGTS <4	
 • Continue study drug at the same dose level (i.e., do not uptitrate) and repeat MRI scan 4 weeks later. 
 – As long as BGTS is <4 and ≥ 1, continue study drug at the same dose level and repeat MRI 4 weeks later. – Once ARIA resolves, resume uptitration and obtain an MRI scan per the titration schedule. For participants randomized to the Q2W regimen, perform another MRI scan 3 months after ARIA resolution.
	Symptomatic ARIA-E (of any size) or asymptomatic ARIA-E and BGTS ≥ 4	
 • Temporarily interrupt study drug and perform MRI scans at 4-week intervals until symptoms and ARIA-E resolve. • When symptoms and ARIA-E resolve, reintroduce study drug at dose given at the time the event was detected. 
 – Perform an MRI scan before next scheduled dose for participants randomized to the Q4W regimen or after the second dose for participant randomized to the Q2W regimen. – If no new ARIA-E is detected, resume uptitration and obtain an MRI per titration schedule. For participants randomized to the Q2W regimen, perform another MRI scan 3 months after study drug reintroduction.
	Any recurrence of ARIA-E	
 • Treat the same as the first event (based on symptoms and BGTS).
ARIA-H	>15 ARIA-H cumulatively (should not include any disseminated LH)	
 • Discontinue study drug.

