4.7 TREATMENT, PARTICIPANT, STUDY, AND SITE DISCONTINUATION

4.7.1 Study Treatment Discontinuation

Participants must discontinue study treatment if they experience any of the following:

- Any medical condition that the investigator or Sponsor determines may jeopardize the participant's safety if he or she continues to receive study treatment
- Investigator or Sponsor determines it is in the best interest of the participant
- Pregnancy
- Upon evidence of more than 15 ARIA-H, cumulatively
- Any disseminated leptomeningeal hemosiderosis

All participants who withdraw from treatment will be asked to return 2 weeks after last dose in order to complete the early termination visit assessments.

In addition, participants who withdraw from treatment will be asked to return for collection of safety (except MRI) and limited efficacy data (i.e., the primary and secondary endpoints) at visits that have efficacy assessments according to the schedule of activities until the end of the double-blind treatment period, *and then the follow-up visits*, or until the last OLE follow-up visit (OLE Follow Up 2) for those who enrolled in the OLE.

The primary reason for study treatment discontinuation should be documented on the appropriate eCRF. Participants who discontinue study treatment prematurely will not be replaced.

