- In exceptional cases of 1) an ARIA-E that is asymptomatic with BGTS < 4 and that is considered stable over consecutive MRI images by the Sponsor and investigator; or 2) symptomatic ARIA-E for which the imaging evidence of ARIA-E has resolved but

the CNS symptoms continue, the study drug can either be reintroduced or uptitrated, as applicable, and 4-weekly MRI monitoring may no longer be necessary, as determined by the Sponsor and investigator.

- Symptomatic ARIA-E is defined as onset or worsening of CNS symptom(s) that is/are temporally associated with ARIA-E MRI findings.
- Any recurrence of ARIA-E: Treat using the same procedures as for the first event (based on symptoms and BGTS).
- Participants who develop > 15 ARIA-H cumulatively will be discontinued from study drug (the cumulative number should not include any disseminated leptomeningeal hemosiderosis, i.e., up to 3 focal leptomeningeal hemosiderosis *either on the same scan or cumulatively*; a focal leptomeningeal hemosiderosis is counted as an ARIA-H).
- In cases where both ARIA-E and ARIA-H occur, the most conservative approach should be followed.
- A PK sample and a plasma biomarker sample will be obtained as soon as is practical (e.g., at an unscheduled visit) once the site becomes aware of the occurrence or worsening of ARIA-E or ARIA-H that meet the discontinuation criteria.
- The investigators may choose to perform additional MRI monitoring for ARIA at any time.
- MRI monitoring of ARIA findings should be conducted at approximately 4-week intervals.
- Any other new significant findings will be reviewed by the medical monitor and appropriate dose action will be taken.

The iDMC reviews the incidence of ARIA in an unblinded manner and may recommend adjustment of dosing regimen and/or ARIA management for the overall study population or for a specific *APOE* ε4 genotype.

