### **5.6.3 Magnetic Resonance Imaging Safety Findings**

ARIA-E and ARIA-H are identified risks associated with gantenerumab. Sites were asked to capture all ARIAs as AEs in the eCRF that met any of the following criteria:

- Symptomatic ARIA-E (i.e., accompanied by CNS symptoms), and/or

- ARIA findings that result in a change in study treatment (e.g., dosage modification, treatment interruption, or treatment discontinuation), and/or
- Findings that are otherwise clinically significant in the investigator’s judgment

Not all ARIA MRI findings qualify as AE. ARIA analyses will be mainly based on ARIA MRI findings. ARIA AEs will also be reported. Based on MRI data, the incidence, and severity (based on the Barkhof Grand Total Score [BGTS]) ARIA-E and the incidence of ARIA-H will be summarized by treatment group and within this also by APOE ε4 genotype (by number of alleles) and by dose level. Additionally, the timing of ARIA-E and the timing to meet the protocol-defined criteria for permanent discontinuation due to ARIA-H will be also summarized by descriptive statistics and eventually by Kaplan-Meier methods. Recurrence of ARIA-E will be summarized by treatment group and within this also by APOE ε4 genotype (by number of alleles). ARIA-E associated with CNS symptoms (see Section 5.6.3.1) and with serious CNS symptoms will be summarized by treatment group and within this also by APOE ε4 genotype. Temporal co-occurrence of ARIA-E and ARIA-H will be summarized by treatment group and within this also by APOE ε4 genotype (by number of alleles). Temporal co-occurrence is defined as an MRI scan showing new ARIA-H that occurs between ARIA-E onset and resolution (inclusive), irrespective of the brain region.

MRI findings other than ARIA will also be summarized.

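### Protocol 5.1.2 and Appendix 6 do not clearly carry the disseminated leptomeningeal hemosiderosis stopping criterion of 4.7.1, so there is no single list of ARIA-H discontinuation criteria

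*Protocol*

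**What the plan says.** **Protocol 4.7.1 (Study Treatment Discontinuation).** The list opens "Participants must discontinue study treatment if they experience any of the following". Two of its bullets concern ARIA-H: "Upon evidence of more than 15 ARIA-H, cumulatively" and, as a separate bullet with no count attached, "Any disseminated leptomeningeal hemosiderosis".

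**Protocol 5.1.2 (Management of Participants Who Experience Selected Adverse Events).** The ARIA-H rule orders discontinuation above 15 cumulative findings. Disseminated LH appears only in the parenthesis to that rule: "the cumulative number should not include any disseminated leptomeningeal hemosiderosis". The parenthesis goes on to mention up to three focal lesions, on one scan or cumulatively, and says that a focal lesion counts as an ARIA-H. Near the end of the list is a general provision: "Any other new significant findings will be reviewed by the medical monitor and appropriate dose action will be taken".

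**Protocol Appendix 6.** There is one ARIA-H row, ">15 ARIA-H cumulatively (should not include any disseminated LH", with the action to discontinue study drug. Neither the table nor its notes give a separate action for disseminated LH.

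**SAP 5.6.3.** In the MRI safety analyses, "the timing to meet the protocol-defined criteria for permanent discontinuation due to ARIA-H will be also summarized". The criteria are not restated there.

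**The concern.** A permanent stopping rule for an identified risk of the drug should read the same wherever a site looks it up. Here the general discontinuation section has two ARIA-H triggers, while the two places written for handling MRI findings plainly state one. The second trigger survives there only as a parenthesis that can be read in two ways.

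The protocol steers sites to those two places:

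- Section 1.3.3 says permanent discontinuation for ARIA follows the plan in 5.1.2.
- Sections 4.3.2.1 and 4.3.2.2 point to 5.1.2 for interruption and discontinuation rules, in the double-blind period and the open-label extension respectively.
- Section 4.6.5 points to 5.1.2 when a new ARIA finding appears.
- Section 5.1.1.1 points to Appendix 6 for ARIA management.

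Neither 5.1.2 nor Appendix 6 refers back to 4.7.1. At stake are consistent handling of the same scan across sites and a clear definition for everything else keyed to the ARIA-H discontinuation criteria.

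**Working it through.** No sample size, power, alpha or event figure is involved, so there is nothing to recompute. The check sets the three rules side by side for the four possible combinations of count and disseminated LH.

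| Counted ARIA-H | Disseminated LH | 4.7.1 | 5.1.2 | Appendix 6 |
|---|---|---|---|---|
| 15 or fewer | No | No ARIA-H stop | No ARIA-H stop | No ARIA-H stop |
| More than 15 | No | Stop | Stop | Stop |
| More than 15 | Yes | Stop | Stop | Stop |
| 15 or fewer | Yes | Stop | Depends on the parenthesis | Depends on the parenthesis |

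The passages can diverge in the last row only. There the outcome turns on the parenthesis:

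1. **Read as not counted.** The finding adds nothing to the tally, so the trigger of more than 15 is not met. In 5.1.2 the remaining route is medical monitor review of other significant findings, with whatever dose action is judged appropriate. Appendix 6 has no such provision and so gives no specific action.
2. **Read as not allowed.** Disseminated LH lies outside what is tolerated, and both places agree with 4.7.1. Even so, neither states that the finding alone leads to discontinuation.

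The wording does not settle which reading is meant. In 5.1.2 the grammatical subject is the cumulative number, and the text goes on to say what counts, which favors the first reading. The mention of up to three focal lesions can also be taken as a ceiling, which favors the second. The imaging exclusion criterion in 4.1.2.2 attaches similar wording to its limit of five findings and is open to the same two readings.

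The following provisions depend on which list is used:

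- **Uptitration (5.1.2):** requires that the ARIA-H discontinuation criteria have not been met.
- **Extra PK and plasma biomarker samples (5.1.2 and the Appendix 6 notes):** triggered by ARIA-H that meets those criteria.
- **SAP 5.6.3:** summarizes time to meeting those criteria. From 4.7.1 a programmer would derive the earlier of two events; from Appendix 6 on the not-counted reading, one event.

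**The case against.** The strongest reply is that this is an omission and not a conflict. Section 4.7.1 is unconditional and binds every site. No passage permits dosing to continue with disseminated LH, and neither 5.1.2 nor Appendix 6 claims to be exhaustive or to override 4.7.1. A site that stops complies with all three. If disseminated LH ends treatment through its own bullet, leaving it out of a tally is also coherent. All of this stands. A reader might infer that 5.1.2 and Appendix 6 set a competing rule that lets treatment continue; the text does not say that. What remains is that a mandatory stop is plainly stated in one place and is missing or ambiguous in the two places to which sites are sent.

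A reader might also infer that 5.1.2 leaves disseminated LH with no action at all. That is too strong. The general provision brings other significant findings to the medical monitor, and 4.6.5 has the site and the Sponsor notified rapidly of any new finding by the central reader. These are real safeguards, but case-by-case review is not the mandatory stop of 4.7.1. The instruction in 5.1.2 to take the most conservative approach does not close the gap, because it applies only when ARIA-E and ARIA-H occur together.

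On the SAP, the reply is that the plural reference to protocol-defined criteria fits the two triggers in 4.7.1, that 4.6.5 bases analysis on central reads, and that the summary is descriptive. Timing could therefore be derived uniformly whatever individual sites did. That is right, provided the analysts settle on one list. The SAP does not name it.

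**Conclusion.** The point holds as an internal inconsistency: the protocol is wrong as written, and this is not a matter of design preference. The lists of ARIA-H stopping criteria differ between 4.7.1 on one side and 5.1.2 and Appendix 6 on the other, unless the parenthesis is read as not allowed, and the text does not compel that reading.

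The scope is participants with disseminated LH and 15 or fewer counted ARIA-H. The documents do not say how many to expect, and the number may be small. No efficacy result, power figure or error rate is affected.

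Two further inferences are not supported. That sites have acted differently on the same scan is a risk drawn from the wording and the cross-references; the documents report no such case. That the reported timing of ARIA-H discontinuation criteria will be distorted is possible but not shown: the SAP effect is an undefined reference in a descriptive summary that can be derived from central reads.

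The point should still be acted on, because the rule governs permanent discontinuation for an identified risk and the correction is small.

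**What to change.** - Reconcile Protocol 4.7.1, 5.1.2 and Appendix 6 so that each carries, or cross-references, one list of ARIA-H discontinuation criteria.
- Reword the parenthesis so that it says plainly whether disseminated LH is only left out of the count or is itself a stopping criterion. Check the similar wording in 4.1.2.2 at the same time.
- Inform sites of the reconciled text.
- Have SAP 5.6.3 cite that list for the timing summary.

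Which clinical rule should apply is for the sponsor and its clinical experts; no view is taken here. The cost is protocol wording, a site communication and one reference in the SAP. No change to the design, sample size or efficacy analysis is needed.

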Appendix 6: Management Rules for Amyloid-Related Imaging Abnormalities (cont.)

ARIA-E = amyloid-related imaging abnormality–edema/effusion; ARIA-H=amyloid-related imaging abnormality–hemosiderin deposition; BGTS=Barkhof grand total score; LH=leptomeningeal hemosiderosis; MRI=magnetic resonance imaging; Q2W=every 2 weeks.

In exceptional cases of (1) an ARIA-E that is asymptomatic with BGTS <4 and considered stable over consecutive MRI images by the Sponsor and investigator; or (2) symptomatic ARIA-E for which the imaging evidence of ARIA-E has resolved but the CNS symptoms continue, study drug can be either reintroduced or uptitrated, as applicable, and 4-weekly MRI monitoring may no longer be necessary, as determined by the Sponsor and investigator.

Symptomatic ARIA-E is defined as onset or worsening of CNS symptom(s) that is/are temporally associated with ARIA-E MRI findings

A PK and a plasma biomarker sample will be obtained as soon as is practical (e.g., at an unscheduled visit) once the site becomes aware of the occurrence or worsening of ARIA-E or of the occurrence of ARIA-H meeting discontinuation criteria

## STATISTICAL ANALYSIS PLAN VERSION HISTORY

This SAP was developed based on Roche SAP model document v2.0, revised 26 October 2020.

SAP Version	Approval Date	Based on Protocol (Version, Approval Date)
3	see electronic date stamp on last page of the document	Version 5.0, 2 August 2021
2	29 July 2022	Version 5.0, 2 August 2021
1	12 October 2021	Version 5.0, 2 August 2021

## **STATISTICAL ANALYSIS PLAN AMENDMENT RATIONALE**

Key changes to the SAP version 2.0, along with the rationale(s) for each change, are summarized below.

Section	Description of Change	Rationale for Change
Section 4	In Table 2 , Neurogranin has been added to the definition of the CSF-longitudinal analysis set	It was a typo not including Neurogranin it in the previous version of the SAP.
Section 5.3.3	In the 'analysis step of the 'description of the primary estimator' the percent relative difference was updated to be defined as 100 times the estimated treatment effect divided by the absolute value of the placebo arm estimate	It was a typo not to considering the 'absolute value' for the denominator in the previous version of the SAP.
Section 5.3.5.2	A new supplementary analysis has been added, 'Treatment effect in relationship to a post-baseline timepoint', to estimate the percent relative difference in CDR-SB between week 52 and week 116, as well between week 24 and week 116 and week 76 and week 116	In order to assess the treatment effect using different starting points relative to the scheduled start of the target dose (with Weeks 24, 52 and 76 being respectively 12 weeks before, 16 weeks after and 40 weeks after the scheduled start of the target dose). This analysis may help to better understand the time dynamics of a treatment effect.
Section 5.3.6	A new section was added to describe what to do in case of the rare circumstances that the imputation model (see step 1, imputation model, in Section 5.3.3 ) would fail to converge.	To add clarity
Section 5.4	More details have been added to describe the estimator used for the secondary efficacy endpoints.	To add clarity
Section 5.4.1	Given that the 'confirmatory secondary endpoints' are a subset of the secondary endpoints, now the SAP is referencing to the secondary endpoints for the details of the estimand's strategy,	To add clarity
Section 5.5	More details have been added to describe the estimator used for the exploratory efficacy endpoints.	To add clarity
Section 5.7.7	The CSF biomarkers analysis plan has been updated to now use two different	Although those two models will provide the same exact p-

	ANCOVA models: one based on the change from baseline and the other one based on the value at visit	value in characterizing the treatment effect, they also allow to estimate complementary summary statistics.
Section 5.7.8	The plasma biomarkers analysis plan has been updated to now use two different MMRM models: one based on the change from baseline and the other one based on the value at visit	Although those two models will provide the same exact p-value in characterizing the treatment effect, they also allow to estimate complementary summary statistics.

Additional minor changes have been made throughout the document to improve clarity and consistency.

## LIST OF ABBREVIATIONS AND DEFINITIONS OF TERMS

Abbreviation or Term	Description
A $\beta$	amyloid-beta
AD	Alzheimer's disease
ADA	anti-drug antibody
ADAS-Cog11 / Cog13	Alzheimer disease assessment scale – cognition, subscale 11 / 13
ADCS-ADL	Alzheimer disease cooperative study - activities of daily living
ADL	activities of daily living
AE	adverse event
AESI	adverse event of special interest
ANCOVA	analysis of covariance
APOE	apolipoprotein $\epsilon$
ARIA-E	amyloid-related imaging abnormalities – edema/effusion
ARIA-H	amyloid-related imaging abnormalities – hemosiderin deposition
CDR-GS	clinical dementia rating – global score
CDR-SB	clinical dementia rating – sum of boxes
CIR	copy increments from reference
CNS	central nervous system
COVID-19	coronavirus disease 2019
CSF	cerebrospinal fluid
CSR	Clinical Study Report
C-SSRS	Columbia-suicide severity rating scale
DTI	diffusion tensor imaging
ECG	Electrocardiogram
eCRF	electronic case report form
EMA	European Medicines Agency
EQ-5D	EuroQoI-Five Dimensions
FAQ	functional activities questionnaire
FDA	(U.S.) Food and Drug Administration
ICE	intercurrent event
ICH	International Council on Harmonization
iDMC	independent Data Monitoring Committee
IRC	independent review charter

## LIST OF ABBREVIATIONS AND DEFINITIONS OF TERMS (Cont'd)

Abbreviation or Term	Description
ISR	injection-site reaction
ITT	intent to treat
IxRS	interactive voice/web-based response system
MAR	missing at random
MedDRA	Medical Dictionary for Regulatory Activities
mITT	modified intent to treat
MMRM	mixed effects model repeated measures
MMSE	mini-mental state examination
MNAR	Missing not at random
MRI	magnetic resonance imaging
NMPA	National Medical Products Administration
NPI-Q	neuropsychiatric inventory-questionnaire
NSDCR	not study drug or condition related
OLE	open-label extension
PET	Positron emission tomography
PK	Pharmacokinetic
pTau	phosphorylated tau
Q2W	every 2 weeks
Q4W	every 4 weeks
QoL	quality of life
QoL-AD	quality of life – Alzheimer's disease
RUD-Lite	resource utilization in dementia - lite
SAE	serious adverse events
SAP	Statistical Analysis Plan
SC	Subcutaneous
SDCR	study drug or condition related
SUV	standard uptake value
SUVR	standard uptake value ratio
tTau	total tau
ZCI-AD	Zarit caregiver interview – Alzheimer's disease

## 1. **INTRODUCTION**

This document describes the statistical analyses that will be reported in the primary Clinical Study Reports (CSR) of Studies WN29922 (hereafter referred to as “GRADUATE I”) and WN39658 (hereafter referred to as “GRADUATE II”). The descriptions, methodology, and analyses presented in this document applies to both studies unless otherwise specified. The efficacy estimands and safety endpoints that will be the basis for comparing the two treatment arms will be defined in full in this document along with the populations of participants that are to be used in the analyses.

This Statistical Analysis Plan (SAP) covers analyses planned for the double-blind treatment period and the safety follow-up across both studies. Analyses for the OLE phase will focus on safety and will be listed directly in the corresponding List of Planned Outputs (LoPO). Pharmacokinetic (PK) data will be reported in a separate population PK report and thus is not covered in this document. Similarly, health economic data (such as utility values derived from the EQ-5D-5L and the RUD-lite) will be analyzed and reported separately from the Clinical Study Report and are therefore not covered in this document.

The description of layouts for the CSR outputs, the details about the underlying analysis datasets and programs, and the linking of production outputs to sections in the CSR are not within the scope of this document and will be covered in separate documents, i.e., Data Analysis Plan Module 2 and 3.

The language used in this SAP supersedes that in the protocol and protocol synopsis.

An early draft of this SAP was presented to U.S. Food and Drug Administration (FDA) in the context of a Type C meeting (Written Response Only procedure, December 21, 2020, Ref ID: [4720726](#)) and to the European Medicines Agency (EMA) in the context of Scientific Advice procedure (EMA Written Advice received on 29 January 2020; [EMA//SA/0000046418](#)). These procedures focused on the proposed primary estimand, the estimator and other aspects of the analysis plan. Both agencies in principle agreed on the primary question of interest in the context of the estimand framework ([ICH E9\[R1\]](#)). There was also agreement on the proposed hierarchy of secondary endpoints.

A more advanced version of the SAP was submitted to the FDA for their review in December 2021. The feedback received during these health authority interactions was duly considered and informed the current version of this SAP.

### 1.1 **OBJECTIVES**

This study will evaluate the efficacy and safety of gantenerumab compared with placebo in participants with early (prodromal to mild) AD.

**Table 1 Objectives and Corresponding Endpoints**

Primary Objective(s)	Corresponding Endpoint(s)

 
To evaluate the efficacy of gantenerumab administered by SC injection compared with placebo
 
	
 
The change in global outcome from baseline (Day 1) to Week 116, as measured by the CDR-SB
 

Secondary Objective(s)	Corresponding Endpoints

 
To evaluate the efficacy of gantenerumab versus placebo on cognition and/or function
 
	
The change from baseline to Week 116 in cognition and/or function, as measured by:
 
 
MMSE total score
 
ADAS-Cog11 and ADAS-Cog13
 
Verbal Fluency Task
 
Coding
 
FAQ
 
ADCS-ADL total score and instrumental score
 

Exploratory Objective(s)	Corresponding Endpoints

 
To evaluate the efficacy of gantenerumab versus placebo
 
	
The change from baseline to Week 116 in the following:
 
 
Clinically evident decline as measured using the CDR
 
Severity, as assessed by the CDR Global Score
 
Dependence level, as derived from the ADCS-ADL score
 
Health-related quality of life, as assessed by the QoL-AD scale
 
Behavioral and neuropsychiatric symptoms of AD, as measured by the NPI-Q
 
Study partner burden, as assessed by the ZCI-AD scale
 
Elements of resource utilization, as assessed by the RUD-Lite
 
Health outcomes in participant and study partner, as measured by EQ-5D questionnaire
 

